6. GENERAL AND STATISTICAL CONSIDERATIONS

6.1. REFERENCE START DATE AND STUDY DAY

Study Day will be calculated from the reference start date and will be used to show start/stop day of assessments and events.

Reference start date (Day 1) is defined as the day of procedure (impression cytology or superficial keratectomy), and will appear in every listing where an assessment date or event date appears.

- If the date of the event is on or after the reference start date, then:

Study Day = (date of event – reference date) + 1.

- If the date of the event is prior to the reference start date, then:

Study Day = (date of event – reference date).

Document: \\ieedc-vnasc01\Biosdata\GSK\GSK2857916\UZA78766\Biostatistics\Documentation\SAP\UZA78766_214098_SAP_v2.0_12OCT2022.docx

Author: PPD

Version Number: 2.0

Version Date: 12OCT2022

Template No.: CS_TP_BS016 Revision 6

Reference: CS_WI_BS005

Effective Date: 02Dec2019

In case of partial/missing dates, they will be handled as specified in APPENDIX 1. Imputed dates will not be used to calculate study day of the events and will not be presented in the listings.

6.2. BASELINE

The baseline value will be the latest assessment with a non-missing value done before the IC or SK procedure, including those from unscheduled visits. If time is not collected, Day 1 assessments are assumed to be taken prior to procedure and used as baseline.

6.3. UNSCHEDULED VISITS

Unscheduled measurements will not be included in tables. Listings will include scheduled and unscheduled visits data.

6.4. STATISTICAL TESTS

No statistical test will be performed.

6.5. MISSING DATA

No imputation of values for missing data will be performed.

6.6. SOFTWARE VERSION

All analyses will be conducted using SAS version 9.4 or higher.

7. OUTPUT PRESENTATIONS

The templates provided with this SAP describe the presentations for this study and therefore the format and content of the summary tables, figures, and listings to be provided by IQVIA Biostatistics.

Document: \\ieedc-vnasc01\Biosdata\GSKGSK2857916\UZA78766\Biostatistics\Documentation\SAP\UZA78766_214098_SAP_v2.0_12OCT2022.docx

Author: PPD Version Number: 2.0

Version Date: 12OCT2022

Template No.: CS_TP_BS016 Revision 6 Reference: CS_WI_BS005

Effective Date: 02Dec2019

Summary statistics will be summarized by visit when appropriate and will consist of values for:

- number of participants, number of missing values, mean, standard deviation, median, lower and upper quartiles, minimum and maximum for quantitative parameters.
- number and percentage of participants for qualitative parameters. Percentages will be presented with one decimal place. Percentages computation will depend on table structure and will be detailed in the table footnotes (See Output templates document).

8. DISPOSITION AND WITHDRAWALS

All participants who provide informed consent will be accounted for in this study.

8.1. DISPOSITION

The number of screened participants, screen failures and reasons of screen failure will be presented on all participants.

CCI

9. DEMOGRAPHIC CHARACTERISTICS

Demographic characteristics will be presented on the all-treated population.

The following demographic data will be reported for this study:

- Age (years) - calculated relative to year of consent
- Sex
- Ethnicity
- Race
- GSK2857916 parent study or patients on commercial prescriptions

Demographic characteristics will be presented in a table by method of tissue collection (impression

Document: \\ieedc-vnasc01\Biosdata\GSKGSK2857916\UZA78766\Biostatistics\Documentation\SAP\UZA78766_214098_SAP_v2.0_12OCT2022.docx

Author: PPD

Version Number: 2.0

Version Date: 12OCT2022

Template No.: CS_TP_BS016 Revision 6

Reference: CS_WI_BS005

Effective Date: 02Dec2019

cytology/superficial keratectomy/not collected).

Demographic characteristics will also be included in a by-participant listing.

9.1. DERIVATIONS

Age (years) = Year of consent – Year of birth

10. OCULAR HISTORY AND RISK FACTORS

The following ocular history and risk factors will be reported for this study:

- Previous diagnosis of dry eye (Yes/No)
- Previous diagnosis of glaucoma on right/left eye (Yes/No)
- Previous diagnosis of cataract on right/left eye (Yes/No)
- History of cataract surgery on right/left eye (Yes/No)
- History of laser treatment surgery on right/left eye (Yes/No)
- History of other ocular surgery on right/left eye (Yes/No)
- History of serious eye trauma on right/left eye (Yes/No)
- History of ocular disease requiring medical treatment on right/left eye (Yes/No)
- Other (Yes/No)

Ocular history and risk factors will be included in a by-participant listing.

11. OCULAR THERAPY

Ocular therapies will be presented in a by-participant listing only on the all-treated population and coded using MedDRA version 25.0 or above.

Concomitant ocular therapies will be flagged and are therapies which:

- started prior to, on or after the date of informed consent,
- AND ended on or after the date of informed consent or were ongoing at the end of the study.

Document: \\ieedc-vnasc01\Biosdata\GSK\GSK2857916\UZA78766\Biostatistics\Documentation\SAP\UZA78766_214098_SAP_v2.0_12OCT2022.docx

Author: PPD Version Number: 2.0

Version Date: 12OCT2022

Template No.: CS_TP_BS016 Revision 6

Reference: CS_WI_BS005

Effective Date: 02Dec2019

12. OCULAR MEDICATION

Ocular medication will be presented in a by-participant listing only on the all-treated population and coded using GSK drug dictionary.

Concomitant ocular medications will be flagged and are medications which:

- started prior to, on or after the date of informed consent,
- AND ended on or after the date of informed consent or were ongoing at the end of the study.

13. DISEASE CHARACTERISTICS

The following disease characteristics will be reported for this study:

- Time since initial diagnosis of multiple myeloma – calculated relative to date of screening
- Stage at screening and at initial diagnosis (I/II/III/Unknown)
- Myeloma immunoglobulin (IgA/IgD/IgE/IgG/IgM)
- Light chain myeloma at screening (Yes/No) and type.

Disease characteristics will be included in a by-participant listing on the all-treated population.

14. MYELOMA TREATMENT

Prior myeloma treatments will be presented in a by-participant listing only on the all-treated population.

15. EXPOSURE TO BELANTAMAB MAFODOTIN

The following exposure information will be reported for this study:

- Duration of exposure (weeks) derived by: (last date of dose intake – first date of dose intake + 1) / 7.

All exposure information will be included in a by-participant listing on the all-treated population.

Document: \\ieedc-vnasc01\Biosdata\GSK\GSK2857916\UZA78766\Biostatistics\Documentation\SAP\UZA78766_214098_SAP_v2.0_12OCT2022.docx

Author: PPD Version Number: 2.0
Version Date: 12OCT2022

Template No.: CS_TP_BS016 Revision 6

Reference: CS_WI_BS005

Effective Date: 02Dec2019

16. PRIMARY ENDPOINT

Data collected from “Corneal Tissue Sample” and “Pathology” eCRF pages will be presented on the EICSK population.

Method of tissue collection will be presented in a table on study eye.

“Immunohistochemistry”, “Electron microscopy” parts from “Pathology” eCRF page will be presented in tables by method of tissue collection (impression cytology/superficial keratectomy) on study eye.

“Anterior segment slit-lamp photography” and “Pathology comments” parts from “pathology” eCRF page will be presented in a by-participant listing.

All Corneal Tissue Sample and Pathology data will also be included in a by-participant listing on the all-treated population.

17. SECONDARY AND EXPLORATORY ENDPOINTS

17.1. SECONDARY AND EXPLORATORY CLINICAL ENDPOINTS

Data collected from “Corneal symptom grading” eCRF page will be presented in a table by method of tissue collection (impression cytology/superficial keratectomy) and by visit on study eye on the ICSK population.

Data collected from “Ocular corneal examination” eCRF page will be presented in a table by method of tissue collection (impression cytology/superficial keratectomy) and by visit on study eye on the ICSK population.

CCI

Safety follow up visit is required for participants with superficial keratectomy procedure but not required for participants with impression cytology unless the participant is experiencing discomfort or an AE. At this visit, the table will present participants with superficial keratectomy procedure and participants with impression cytology who have had at least one safety follow-up visit.

For by-visit tables, if two safety follow-up visits have been done, the latest non-missing value will be considered

Document: \\ieedc-vnasc01\Biosdata\GSK\GSK2857916\UZA78766\Biostatistics\Documentation\SAP\UZA78766_214098_SAP_v2.0_12OCT2022.docx

Author: PPD

Version Number: 2.0

Version Date: 12OCT2022

Template No.: CS_TP_BS016 Revision 6

Reference: CS_WI_BS005

Effective Date: 02Dec2019

only.

All secondary and exploratory clinical data will also be included in a by-participant listing on the all-treated population. Unscheduled visits will be displayed in these listings.

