2.3. Benefits and Risks

CCI

Pain:

The SK procedure can cause pain to the participant but is generally safe and well tolerated. Pain can be managed by the use of artificial tears or a bandage contact lens

Infection:

The SK procedure carries a risk of infection and requires prophylactic antibiotics. Infectious keratitis occurs in 2% of patients [Vo, 2015]. These data are from patients who underwent epithelial debridement and diamond burr polishing of the Bowman's membrane (n=91 eyes).

Delayed Healing:

In this study, it is anticipated that SK-induced epithelial defect will heal within 7 days with the use of a bandage contact lens.

Typically, healing occurs in 2 days for a 3–4 mm central epithelial debridement [Sta Iglesia, 2000] [Wilson, 2004] [Park, 2019]. Temporary scarring/subepithelial haze can occur in 21% of eyes at 1 month post procedure and in 9% of eyes at last follow-up and is not visually significant. No complications resulting in impaired vision at final follow-up have been reported [Vo, 2015] [Murueta-Goyena, 2018].

Comorbidities such as diabetes and dry eye can significantly delay the healing process and may require adjuvant therapy (e.g., bandage contact lens).

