6.4. Superficial Keratectomy Procedure

The study eye will be selected using the criteria described above. Following topical anesthesia (such as proparacaine hydrochloride 0.5%) and a drop of povidone iodine 5% for antisepsis, an eyelid speculum will placed. The eye will then be visualized using a slit-lamp or operating microscope in a procedure room. The corneal epithelium of interest (the region that contains the MECs) will be carefully removed using either a Weck-Cel/dry cellulose sponge or small blade; Jeweler or 0.12 forceps may be required in some cases. The tissue will be submitted in formalin for histologic analysis. Care should be taken to minimize crush artefact to the epithelium and to avoid damage to Bowman layer.

Post procedure, another drop of povidone iodine 5% will be placed, followed by a drop of balanced salt solution or topical anesthetic (to wash out any residual povidone-iodine). A bandage contact lens will be placed.

[figure not shown]
It is recommended that a topical antibiotic and a topical steroid (or a fixed combination of both) is prescribed 4 times per day, each, for at least one week (or longer), until the epithelial defect is documented as healed and the bandage contact lens is no longer required in the assessment of treating Ophthalmologist. The topical antibiotic may be discontinued once the epithelial defect has healed. The topical steroid should be tapered off over the following two weeks.

The expected time for corneal re-epithelialization is 7–10 days [Ashby, 2014]. The procedure can cause some pain to the participant but is generally safe and well tolerated. Pain, if any, can be managed by the use of artificial tears. A bandage contact lens should be helpful in reducing the need for pain medication. In participants with symptomatic blurred vision, the procedure may result in temporary visual improvement. The procedure may also be complicated by an infection or worsening vision. An ocular pathologist will be consulted to determine the appropriate testing of tissue sample.

[figure not shown]
If the epithelial defect has not healed completely at the day 7 visit, the bandage contact lens should be left in place and both the steroid and antibiotic continued. The participant should be examined again in approximately 1 week.

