9.3. Analysis Methods

No formal statistical tests of hypothesis will be performed. All participants who have SK in this program will be included in the safety analysis.

Demographic characteristics and dosing level and duration will be summarized using descriptive statistics (i.e., categorical variables will be described by absolute and relative frequencies), while continuous variables will be summarized by mean, standard deviation, quartiles, minimum, and maximum. The available information on all nonserious AEs leading to discontinuation, SAEs, and all other AEs (including AEs of special interest) will also be summarized using descriptive statistics.

All available demographic and safety data will be included in the data listings and tabulations. No imputation of values for missing data will be performed. Participants who

are lost to follow-up will be included in the statistical analysis to the point of their last examination. All data will be examined using standard data management operating procedures.

Changes in corneal epithelial findings from pre to post procedure, pathological and ^{CCI} [REDACTED] results in safety population will be tabulated in a descriptive manner.

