2.2. SECONDARY OBJECTIVES

The secondary objectives are:

- To correlate clinical data, including visual acuity and symptoms, as well as grade and appearance of corneal changes on imaging, with histopathologic findings.
- To describe safety profile of the impression cytology (IC) or superficial keratectomy (SK) procedure.

CCI

Document: \\ieedc-vnasc01\Biosdata\GSK\GSK2857916\UZA78766\Biostatistics\Documentation\SAP\UZA78766_214098_SAP_v2.0_12OCT2022.docx

Author: PPD

Version Number: 2.0

Version Date: 12OCT2022

Template No.: CS_TP_BS016 Revision 6

Reference: CS_WI_BS005

Effective Date: 02Dec2019

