3.2. SCHEDULE OF ACTIVITIES

Procedure	Screening	Pre-IC or SK procedure	IC or SK procedure (day of procedure)	Post-IC or SK procedure*	Safety follow-up (up to 1 week after SK procedure)	Safety follow-up (2 weeks after SK procedure) ^t	Additional follow-up at ophthalmologist's discretion ^s
Informed consent	X						
Eligibility criteria	X						
Slit-lamp examination and confocal microscopy (if available) ^a with imaging		X			X ^d		
Snellen eye test ^a			X		X	X	
CCI							
Corneal tissue sampling ^c			X				
Pathology review of corneal sample				X			
Ophthalmology post-procedure checkup							X
Vital signs (pulse and blood pressure)			X				
AEs/SAEs			X	X	X	X	
Data Collection ^b	X	X	X	X	X	X	X
CCI							

AE, adverse event; CCI

IC, impression cytology; SAE, serious adverse event; SK, superficial keratectomy.

Document: \\ieedc-vnasc01\Biosdata\GSK\GSK2857916\UZA78766\Biostatistics\Documentation\SAP\UZA78766_2140
 98 SAP v2.0 12OCT2022.docx
 PPD

Author:

Version Number: 2.0

Version Date: 12OCT2022

Template No.: CS_TP_BS016 Revision 6

Reference: CS_WI_BS005

Effective Date: 02Dec2019

^a An ophthalmic examination that includes best-corrected visual acuity, slit-lamp examination, and confocal microscopy (if available) must be performed prior to the impression cytology or keratectomy procedure to document site and size of corneal epithelial changes and to correlate imaging with pathologic findings. The slit lamp examination must include orbit/lid/adnexa, conjunctiva, sclera, cornea, anterior chamber, iris, lens, and anterior vitreous. Confirmatory anterior segment photography is also required unless acceptable corneal images are available from an examination performed <14 days prior to impression cytology or SK. It is recommended that the imaging examination be performed at least 24 hrs prior to the procedure.

^b Examples of preferred terms (CTCAE v5.0) include, but are not limited to, keratitis, eye disorder–other, blurred vision, dry eye, eye pain, flashing lights, photophobia, and watering eyes.

^c GSK may store samples for up to 3 years after the end of the study to achieve study objectives. Additionally, with participants' consent, samples may be used for further research by GSK or others such as universities or other companies to contribute to the understanding of the pathophysiology of belantamab mafodotin – associated keratopathy, the development of related or new treatments, or research methods.

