^d Preferred timing for follow-up slit-lamp examination is 24–48 hours post SK procedure but must be performed within 1 week after SK procedure. Safety follow-up after impression cytology is not required unless the participant is experiencing discomfort or an AE.

^e The AE/SAE follow-up immediately after the Post-IC or SK procedure can be done by phone, in the 24–48 hours post-procedure.

^f The participant should be reexamined 2 weeks after the SK procedure if the epithelial defect does not heal completely in the first follow-up. Otherwise, this follow-up is not required.

^g In the event the cornea has not healed at 2 weeks, additional follow-up should be conducted at the ophthalmologist's discretion until healing is confirmed.

^h Minimal additional data will be collected to adequately characterize the development of the corneal epithelial changes in participating patients.

CCI

Document: \\ieedc-vnasc01\Biosdata\GSK\GSK2857916\UZA78766\Biostatistics\Documentation\SAP\UZA78766_214098_SAP_v2.0_12OCT2022.docx

Author: PPD

Version Number: 2.0

Version Date: 12OCT2022

Reference: CS_WI_BS005

[figure not shown]
Template No.: CS_TP_BS016 Revision 6

Effective Date: 02Dec2019

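### SAP 17.1 merges the two scheduled superficial keratectomy safety follow-ups into one table row, so the time point tabulated depends largely on whether the eye had healed

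*SAP*

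**What the plan says.** The schedules of activities in Protocol 1.3 and SAP 3.2 have two safety follow-up columns after SK, one for up to 1 week and one for 2 weeks. Footnote f in SAP 3.2 makes the second conditional: "The participant should be reexamined 2 weeks after the SK procedure if the epithelial defect does not heal completely in the first follow-up". If the eye has healed, the visit is not required. Protocol 6.4 describes the same step from the day 7 visit: "The participant should be examined again in approximately 1 week".

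SAP 17.1 plans tables of corneal symptom grading and of the ocular corneal examination. They are by visit and by method of tissue collection, on the study eye, in participants who had a sample taken. It refers to the safety follow-up as one visit and adds that "if two safety follow-up visits have been done, the latest non-missing value will be considered". SAP 6.3 states separately: "Unscheduled measurements will not be included in tables".

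The row "Snellen eye test" is marked at both safety follow-ups. Slit-lamp examination is marked, after the procedure, only at the first. A secondary objective in SAP 2.2 begins: "To correlate clinical data, including visual acuity and symptoms". Protocol 9.3 promises a descriptive tabulation of "Changes in corneal epithelial findings from pre to post procedure".

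**The concern.** A by-visit table should show what was found at each visit. Here two scheduled visits share a row, and the participant's own recovery largely decides which one supplies the value. A participant healed at the first follow-up normally contributes a first-week value. A participant not healed normally contributes a 2-week value, and the first-week value leaves the table.

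Describing the safety of the procedure is a secondary objective, and early post-procedure status is part of that description. If unhealed eyes improve between the two visits, the row understates the early findings. If the pre-to-post change in Protocol 9.3 uses this value, it inherits the mixture. With few SK participants expected, one or two replacements can alter the row visibly.

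**Working it through.** The plan states no figure on this point, so there is nothing to reproduce. The check follows the rule through the schedule and then shows how its size would scale.

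**1. Which visits the rule acts on.** SAP 6.3 keeps unscheduled measurements out of tables. The discretionary visits after 2 weeks have their own column and are not labelled safety follow-ups. The rule therefore concerns the two scheduled safety follow-ups.

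**2. What each participant contributes, for a variable that can be recorded at both visits.**
- Healed at the first visit, no second visit: first-week value.
- Not healed, value recorded at the second visit: 2-week value, first value dropped.
- Not healed, second value missing: first-week value.
- Healed, but attended the second visit anyway: 2-week value, first value dropped.

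Because the second visit is required only after incomplete healing, the dropped values come mainly, though not necessarily only, from participants not healed at the first visit.

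**3. Which variables are exposed.** Snellen acuity is the only clinical assessment visibly marked at both visits, and no acuity table appears in the public text. Slit-lamp findings are exposed only if the 2-week re-examination is entered on the ocular corneal examination page. The symptom-grading schedule is not visible. Adverse events are marked at both visits but follow the separate worst-grade rule in SAP 17.2.1.

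**4. How far apart the values are.** With the procedure on Day 1 (SAP 6.1), 1 week after is Day 8 and 2 weeks after is Day 15, a nominal gap of 15 − 8 = 7 days. If the first visit falls at the preferred slit-lamp time of 24–48 hours, the nominal gap is 14 − 2 = 12 to 14 − 1 = 13 days. No windows are given, and Protocol 6.4 says only approximately 1 week, so 7 days is not a lower bound.

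**5. How many participants.** This is not derivable. Protocol 2.3 says "Typically, healing occurs in 2 days for a 3–4 mm central epithelial debridement" and, in the same section, anticipates healing within 7 days. Protocol 6.4 expects 7–10 days. Depending on the figure and on the day of the first visit, few or most SK eyes would be unhealed at that visit.

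**6. Size, with assumed counts.** Let n be the SK participants in the row, k those with a value at both visits, and d the mean difference between their two values. The shift in the row mean is (k/n) × d:
- k = 1: 0.20d for n = 5; 0.10d for n = 10.
- k = 2: 0.40d for n = 5; 0.20d for n = 10.

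For a yes/no finding that clears in all k, the percentage shown falls by 100 × k/n points: 40 points for 2 of 5 and 20 points for 2 of 10.

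A worked case, all values assumed: acuity worsening in logMAR is 0 in three healed participants, and 0.3 at the first visit and 0.1 at 2 weeks in two unhealed ones. The first-visit mean is (2 × 0.3)/5 = 0.12. The merged row shows (2 × 0.1)/5 = 0.04. The difference is 0.4 × 0.2 = 0.08.

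If each of 5 SK participants independently has probability p of having both values, the chance that at least one first-visit value is dropped is 1 − (1 − p)^5. This is 0.41 for p = 0.1, 0.67 for p = 0.2 and 0.92 for p = 0.4. The expected number dropped is 5p, that is 0.5, 1 and 2. With separate rows it is 0.

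**The case against.** The strongest reply is that no affected table can be pointed to. Slit-lamp findings recorded on schedule have one post-procedure safety value, so the latest value is the first and nothing is lost. Acuity has no visible table, part of SAP 17.1 is redacted, and the templates named in SAP 7 are not available. This stands as a limit on scope. It does not remove the point, because a rule for choosing between two values acts only where two values exist, and there it has the effect described.

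A second reply is that one last-status value per participant is a recognised summary. That is true, but such a row should be labelled as last status and not presented as a visit.

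A third is that the consequence is small. That also stands: SAP 6.4 rules out tests, all values remain in by-participant listings, and with SK numbers near the target of 5 evaluable samples the listings can be read directly.

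A reader might infer that the rule makes recovery look better than it was. The documents do not establish this. Protocol 6.4 names infection and worsening vision as possible complications, and where an eye is worse at 2 weeks the latest value shows the worse state. A reader might also infer that the loss is sharply selective. With a first visit at 24–48 hours and healing taking 7–10 days, most SK participants could be unhealed, and the loss would then be common and less selective.

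**Conclusion.** The point holds as a minor one. For any variable with values at both SK safety follow-ups, the by-visit table drops the first value mainly in participants not yet healed and combines two time points under one label. No other section reverses this for the tables.

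It rests on reading the rule as covering the two scheduled visits, which SAP 6.3 supports, and on at least one tabulated variable being recorded at both, which the public text does not confirm. The shift of (k/n) × d is exact, but k, n and d are assumed. The documents fix neither the number of SK participants nor the share unhealed. The statement that early findings are understated is conditional on unhealed eyes improving between visits.

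Two further inferences go beyond the text. One is that the replaced value is always at least 7 days older, which is only nominal. The other is that the 2-week data come solely from unhealed participants. The visit is not required after healing, but it is not barred. The primary endpoint and the adverse event tables are unaffected.

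**What to change.** In SAP 17.1 and the table shells, replace the latest-value rule with separate rows for the up-to-1-week and the 2-week safety follow-up, each with its own n. Add a footnote that the 2-week visit was required only for SK participants not completely healed at the first follow-up. The footnote should not claim that the row contains only such participants. If a single value per participant is also wanted, for example for the pre-to-post change, show it as an additional row labelled as the last safety follow-up.

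The change needs no new data and no protocol amendment. Its cost is a slightly longer table with small counts in the 2-week row. The first row would still span the first week, which its label makes plain. The differing healing times in Protocol 2.3 and 6.4 must be reconciled, but that is a separate protocol matter and not part of this fix.
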